### **13.1.2.2 Documentation of Serious Adverse Events**

All SAEs that occur after obtaining informed consent and assent (where applicable) through the Safety Follow-up Visit, regardless of causality, will be reported by the investigator to Vertex GPS. In addition, all SAEs that occur after the Safety Follow-up Visit and are considered related to LUM/IVA will be reported to Vertex GPS **within 24 hours**.

SAEs will be recorded on the Vertex Organized Safety Information Collection Form (hereafter referred to as the “SAE Form”) using a recognized medical term or diagnosis that accurately reflects the event. SAEs will be assessed by the investigator for relationship to the LUM/IVA and possible etiologies. On the SAE Form, relationship to LUM/IVA will be assessed only as related (includes possibly related) or not related (includes unlikely related), and severity assessment will not be required. For the purposes of study analysis, if the event has not resolved at the end of the study reporting period, it will be documented as ongoing. For purposes of regulatory safety monitoring, the investigator is required to follow the event to resolution and report to Vertex the outcome of the event using the SAE Form.

### **13.1.2.3 Reporting Serious Adverse Events**

The investigator is responsible for notifying the sponsor within 24 hours of identifying an SAE, regardless of the presumed relationship to the LUM/IVA. The SAE Form will be completed for new/initial events as well as to report follow-up information on previously reported events. Investigators are asked to report follow-up information as soon as it becomes available to ensure timely reporting to health authorities.

Please send completed SAE Forms to Vertex GPS via  
Email: [REDACTED] (Preferred Choice)  
Or via Fax: [REDACTED]  
Contact Telephone: [REDACTED]

### **13.1.2.4 Expedited Reporting and Investigator Safety Letters**

Vertex, as study sponsor, is responsible for reporting suspected, unexpected, serious adverse reactions (SUSARs) involving the LUM/IVA to all regulatory authorities and participating investigators in accordance with ICH Guidelines and/or local regulatory requirements, as applicable. In addition, Vertex, or authorized designee, will be responsible for the submission of safety letters to central independent ethics committees (IECs).

It is the responsibility of the investigator or designee to promptly notify the local institutional review board (IRB)/local IEC of all unexpected serious adverse drug reactions involving risk to human subjects.

## **13.2 Administrative Requirements**

### **13.2.1 Ethical Considerations**

The study will be conducted in accordance with the current ICH GCP Guidelines, which are consistent with the ethical principles founded in the Declaration of Helsinki, and in accordance with local applicable laws and regulations. The IRB/IEC will review all appropriate study documentation to safeguard the rights, safety, and well-being of the subjects. The study will only be conducted at sites where IRB/IEC approval has been obtained. The protocol, Investigator's Brochure, sample ICF, advertisements (if applicable), written information given to the subjects (including diary cards), safety updates, annual progress reports, and any revisions to these documents will be provided to the IRB/IEC by the investigator or Vertex, as allowable by local applicable laws and regulations.

### **13.2.2 Subject Information and Informed Consent**

After the study has been fully explained, written informed consent will be obtained from the subject or legal representative or guardian (if applicable), and assent will be obtained from the subject (if applicable), before study participation. The method of obtaining and documenting the informed consent and assent (if applicable) and the contents of the consent will comply with ICH GCP and all applicable laws and regulations and will be subject to approval by Vertex or its designee.

### **13.2.3 Investigator Compliance**

No modifications to the protocol will be made without the approval of both the investigator and Vertex. Changes that significantly affect the safety of the subjects, the scope of the investigation, or the scientific quality of the study (i.e., efficacy assessments) will require IRB/IEC notification before implementation, except where the modification is necessary to eliminate an apparent immediate hazard to human subjects. Vertex will submit all protocol modifications to the required regulatory authorities.

When circumstances require an immediate departure from procedures set forth in the protocol, the investigator will contact Vertex to discuss the planned course of action. If possible, contact will be made before the implementation of any changes. Any departures from the protocol will be fully documented in the source documentation and in a protocol deviation log.

### **13.2.4 Access to Records**

The investigator will make the office and/or hospital records of subjects enrolled in this study available for inspection by Vertex or its representative at the time of each monitoring visit and for audits. The records will also be available for direct inspection, verification, and copying, as required by applicable laws and regulations, by officials of the regulatory health authorities (FDA and others). The investigator will comply with applicable privacy and security laws for use and disclosure of information related to the research set forth in this protocol.

### **13.2.5 Subject Privacy**

To maintain subject confidentiality and to comply with applicable data protection and privacy laws and regulations, all eCRFs, study reports, and communications relating to the study will identify subjects by assigned subject numbers and access to subject names linked to such numbers shall be limited to the site and the study doctor and shall not be disclosed to Vertex. As required by applicable laws and regulations in the countries in which the study is being conducted, the investigator will allow Vertex and/or its representatives access to all pertinent medical records to allow for the verification of data gathered in the eCRFs/SAE forms and the review of the data collection process. The FDA and regulatory authorities in other jurisdictions, including the IRB/EC, may also request access to all study records, including source documentation, for inspection.

For sites participating in the study in the US, and in accordance with the Health Insurance Portability and Accountability Act and associated regulations (HIPAA), an executed HIPAA authorization shall be obtained by the site from each subject (or the legal representative of the subject) before research activities may begin. Each HIPAA authorization shall comply with all HIPAA requirements including authorization allowing the site access to and use of the subject's personally identifiable health information, authorization for the site to disclose such information to Vertex, the FDA and other parties requiring access under the protocol, and statements as to the purpose for which such information may be used and for how long.

### **13.2.6 Record Retention**

The investigator will maintain all study records according to ICH GCP guidelines and/or applicable local regulatory requirement(s), whichever is longest, as described in the Clinical Trial Agreement. If the investigator withdraws from the responsibility of keeping the study records, custody will be transferred to a person willing to accept the responsibility and Vertex will be notified.

### **13.2.7 Study Termination**

At any time, Vertex may terminate this study in its entirety or may terminate this study at any particular site. In addition, for reasonable cause, either the investigators or their IRBs/IECs may terminate the study at their center.

Conditions that may lead to reasonable cause and warrant termination include, but are not limited to:

- Subject or investigator noncompliance
- Unsatisfactory subject enrollment
- Lack of adherence to protocol procedures

- Lack of evaluable and/or complete data
- Potentially unacceptable risk to study subjects
- Decision to modify drug development plan
- Decision by the FDA or other regulatory authority

Written notification that includes the reason for the clinical study termination is required.

### **13.3 Data Quality Assurance**

Vertex or its designated representative will conduct a study site visit to verify the qualifications of each investigator, inspect clinical study site facilities, and inform the investigator of responsibilities and procedures for ensuring adequate and correct study documentation.

The investigator is required to prepare and maintain adequate and accurate case histories designed to record all observations and other data pertinent to the study for each study participant. Study data for each enrolled subject will be entered into an eCRF by study site personnel using a secure, validated web-based electronic data capture (EDC) application. Vertex will have read-only access to site-entered clinical data in the EDC application.

Instances of missing, discrepant, or uninterpretable data will be queried with the investigator for resolution. Any changes to study data will be made to the eCRF and documented in an audit trail, which will be maintained within the clinical database.

### **13.4 Monitoring**

Monitoring and auditing procedures developed or approved by Vertex will be followed to comply with GCP guidelines. On-site checking of the eCRFs/SAE Forms for completeness and clarity, cross-checking with source documents, and clarification of administrative matters will be performed.

The study will be monitored by Vertex or its designee. Monitoring will be done by personal visits from a representative of Vertex or designee (study site monitor), who will review the eCRFs/SAE Forms and source documents. The study site monitor will ensure that the investigation is conducted according to the protocol design and regulatory requirements.

### **13.5 Electronic Data Capture**

Vertex will provide the study sites with secure access to and training on the EDC application sufficient to permit study site personnel to enter or correct information in the eCRFs on the subjects for which they are responsible.

[figure not shown]
An eCRF will be completed for each enrolled study subject. It is the investigator's responsibility to ensure the accuracy, completeness, clarity, and timeliness of the data reported in the subject's eCRF. Source documentation supporting the eCRF data will indicate the subject's participation in the study and will document the dates and details of study procedures, AEs, other observations, and subject status.

The investigator, or designated representative, will complete the eCRF as soon as possible after information is collected.

The audit trail entry will show the user's identification information and the date and time of any correction. The investigator will provide formal approval of all the information in the eCRFs,

including any changes made to the eCRFs, to endorse the final submitted data for the subjects for whom the investigator is responsible.

Vertex will retain the eCRF data and corresponding audit trails. A copy of the final archival eCRF in the form of a CD or other electronic media will be placed in the investigator's study file.

3 INTRODUCTION

This statistical analysis plan (SAP) Methods describes the final analysis for Study VX15-809-114 and is based on the following:

- approved clinical study protocol (Version 2.0, dated 19 October 2016)
- approved electronic case report form (eCRF) (Version 2.0, dated 22 December 2016)

Study VX15-809-114 is a Phase 4, open-label treatment, randomized, multicenter, 2-arm, parallel-group, pilot study of adherence to lumacaftor/ivacaftor (LUM/IVA) in cystic fibrosis (CF) subjects homozygous for *F508del*.

This study was terminated early by a business decision. The collected data at the time of termination are limited and therefore, the planned statistical analyses in the protocol will not be performed. Descriptive summary of statistics will be performed. Please refer to Section 8 for details.

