Study Duration	The total duration is approximately 56 weeks (up to 28 days for the Screening Period, 48 weeks for the Treatment Period, and 28 days ( $\pm$ 7 days) for Safety Follow-up Period, if applicable)
Study Design	
This is a Phase 4, open-label, randomized, multicenter, 2-arm, parallel-group pilot study evaluating LUM/IVA adherence. Each study arm will include a smart technology with either active or inactive dosing alert features.
 
This study includes:
 

Screening Period (Day -28 through Day -1)

Treatment Period (Day 1 through Week 48)

Safety Follow-up Visit at Week 52 (28 [<math>\pm</math> 7] days after the final dose of LUM/IVA)

 
Approximately 75 subjects will be enrolled in this study. All subjects will receive LUM 400 mg/IVA 250 mg q12h through Week 48.
 
Subjects will be stratified by age (<23 versus <math>\geq</math>23 years of age) and forced expiratory volume in 1 second (FEV1) severity (<70% versus <math>\geq</math>70% predicted) determined at the Screening Period and then randomized (2:1) to 1 of the following 2 smart adherence technology study arms:
 

Study Arm A: Smart Pill Bottle, activated

Study Arm B: Smart Pill Bottle (control), de-activated alerts and feedback features

 
Subjects will receive standardized education on the benefit of LUM/IVA, LUM/IVA adherence, and training on the use of the assigned smart adherence technology. During applicable study visits, subjects will complete adherence and technology satisfaction assessments. Physicians will also complete a technology satisfaction questionnaire adherence assessments.

**Assessments** **Adherence:** Smart Adherence Technology-Reported Adherence

[REDACTED]

[REDACTED]

[REDACTED]

[REDACTED]

**Safety:** Adverse events, ophthalmologic examinations, clinical laboratory assessments, vital signs, physical examinations

[REDACTED]

**Statistical Analyses** Statistical analysis details will be provided in the Statistical Analysis Plan (SAP).

The primary endpoint is the mean percentage adherence to LUM/IVA treatment over 48 weeks. Assuming a standard deviation (SD) of 8, a sample size of 50 subjects in Study Arm A and 25 in Study Arm B will have 80% power to detect a treatment difference of 5.6% between the means of the 2 arms using a 2-sided, 2-sample t-test at the 0.05 significance level.

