### **10.3 Method of Assigning Subjects to Treatment Groups**

Approximately 75 subjects who meet the eligibility criteria will be randomized at 2:1 ratio to 1 of 2 study arms. All subjects will receive LUM/IVA. Subjects will be stratified by age ( $<23$  versus  $\geq 23$  years of age) and FEV1 severity ( $<70\%$  versus  $\geq 70\%$  predicted) determined at the Screening Visit.

An interactive web response system (IWRS) will be used to assign subjects to study arms. Detailed instructions for randomization will be provided separately.

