### **12.1 Sample Size and Power**

A total of approximately 75 subjects will be enrolled and will be randomized at 2:1 ratio to 1 of 2 study arms: Study Arm A (approximately 50 subjects) and Study Arm B, (approximately 25 subjects).

The primary endpoint is the mean percentage adherence to LUM/IVA treatment over 48 weeks. Assuming a standard deviation (SD) of 8, a sample size of 50 in Study Arm A and 25 in Study Arm B will have 80% power to detect a difference of 5.6% between the means for the 2 study arms using a 2-sided, 2-sample *t*-test at the 0.05 significance level.

Data from studies VX09-809-102, VX12-809-103, and VX12-809-104 were used for this sample size calculation. Sample sizes based on a range of SDs [REDACTED].

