4 STUDY OBJECTIVES

4.1 Primary Objective

To evaluate the impact of smart adherence technology for monitoring of LUM/IVA adherence rates among subjects 16 years of age and older with CF who are homozygous for the *F508del-CFTR* mutation

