8.3.2 Analysis of Adherence Endpoints

Mean percentage adherence to LUM/IVA treatment over treatment duration for all subjects

The percentage adherence over treatment duration for each subject is defined as:

$$100 \times (\text{total number of smart bottle openings over the eligible treatment duration excluding the physician-directed interruption periods of the eligible treatment duration}) / [2 \times (\text{eligible duration of treatment} - \text{the number of physician-directed interruption days of the eligible treatment duration})]$$

Note: (1) the physician-directed interruption is defined as the reported interruptions due to reasons not being “Non-compliance”; (2) if there are more than 2 smart bottle openings at any day, they will be counted as 2 in calculation of the adherence endpoints. (3) the eligible treatment duration = eligible date of last dose – date of first dose + 1, where the eligible date of last dose is defined to be either the CRF collected date of last dose or the last activity date of smart bottle data, whichever is earlier.

Descriptive statistics will be provided by the number of subjects (n), mean, SD, SE, median, min, and max by treatment arm based on FAS. [REDACTED]

The percentage adherence will also be listed.

Mean percentage adherence to LUM/IVA treatment over 0 through 12 weeks for subjects who have at least 12 weeks of eligible smart pill bottle data

Subjects who have at least 12 weeks of eligible smart pill bottle data are defined as those who have at least 12 weeks of eligible treatment duration = eligible date of last dose – date of first dose + 1, where the eligible date of last dose is defined to be either the CRF collected date of last dose or the last activity date of smart bottle data, whichever is earlier.

The percentage adherence over 12 weeks for each eligible subject is defined as:

$$100 \times (\text{total number of smart bottle openings over the first 12 weeks excluding the physician-directed interruption periods of the first 12 weeks}) / [2 \times (12 \text{ weeks (ie, 84 days)} - \text{the number of physician-directed interruption days of the first 12 weeks})]$$

Note: (1) the physician-directed interruption is defined as the reported interruptions due to reasons not being “Non-compliance”; (2) if there are more than 2 smart bottle openings at any day, they will be counted as 2 in calculation of the adherence endpoints.

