Descriptive statistics will be provided by the number of subjects (n), mean, SD, SE, median, min, and max by treatment arm based on FAS. [REDACTED]

The percentage adherence will also be listed.

In addition, the number of smart bottle openings during the physician-directed interruption periods will be presented in a by-subject listing. Please note that if there are more than 2 smart bottle openings at any day, they will be counted as the actual number in this listing.

Further exploratory analyses may be performed if deemed necessary and sufficient data is available.

Proportion of subjects with $\geq 80\%$ (or 90%) adherence 0 through 12 weeks for subjects who have at least 12 weeks of eligible smart pill bottle data

For each eligible subject, the percentage of adherence over 12 weeks will be calculated as described above. The proportion of subjects with $\geq 80\%$ adherence rate over 12 weeks and the proportion of subjects with $\geq 90\%$ adherence rate over 12 weeks will be presented in a summary table.

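### For the stopped study, the SAP's visible text prespecifies no between-arm difference or confidence interval for adherence: clear for the two 12-week proportions, conditional for the means

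*SAP*

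**What the plan says.** The protocol planned between-arm models. Section 12.3.4.1 has an ANCOVA with study arm as a fixed effect for mean adherence over 48 weeks. Section 12.3.4.2 has a logistic model for the proportions with at least 80% adherence, with an odds ratio and its 95% CI.

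The SAP was written after a business decision ended the study. Section 3 gives limited data as the reason that "the planned statistical analyses in the protocol will not be performed. Descriptive summary of statistics will be performed". Section 8.3.1 repeats that the four remaining adherence endpoints get a descriptive summary. The primary objective in section 4.1 is still "To evaluate the impact of smart adherence technology for monitoring of LUM/IVA adherence rates".

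Section 8.3.2 then sets out the reporting:

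- **Mean adherence, over any treatment duration and over 12 weeks.** "Descriptive statistics will be provided by the number of subjects (n), mean, SD, SE, median, min, and max by treatment arm based on FAS". A redaction follows this sentence each time.
- **Proportions with at least 80% and at least 90% adherence over 12 weeks.** The commitment ends: "adherence rate over 12 weeks will be presented in a summary table". This paragraph shows no redaction and does not say that the table is split by arm.

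Two rules decide what an arm means in these tables. Section 7 groups the Full Analysis Set by the technology received, not by the arm assigned. Section 8.1 counts as Arm B any subject whose bottle malfunctioned, who never received alerts and who was then switched to control.

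**The concern.** In a randomised two-arm study, the impact of the activated bottle is a difference between the arms. The SAP keeps that objective, but its visible text stops at summaries. Sparse data are a good reason to give up hypothesis tests and a covariate-adjusted model. They are a poor reason to give up the unadjusted contrast, because a small sample is where the imprecision most needs to be shown.

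Without an interval, readers will compare two means or two percentages by eye. A chance gap can then pass for an effect, and a small gap for evidence of no effect. For the proportions, the visible text does not even guarantee that both arms' percentages appear.

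**Working it through.** **Inputs.** The protocol gives the design as "Approximately 75 subjects who meet the eligibility criteria will be randomized at 2:1 ratio to 1 of 2 study arms" (section 10.3). Section 12.1 gives the sizing: "Assuming a standard deviation (SD) of 8, a sample size of 50 in Study Arm A and 25 in Study Arm B", with "80% power to detect a difference of 5.6% between the means for the 2 study arms". The synopsis gives the test: "using a 2-sided, 2-sample t-test at the 0.05 significance level". The documents do not give the number enrolled at termination, so any size below 50/25 is an assumption.

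**The plan's own figure.**

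- SE of the difference = 8 × √(1/50 + 1/25) = 8 × √0.06 = 1.96 points.
- Noncentrality = 5.6 / 1.96 = 2.86, with 73 degrees of freedom.
- Power = 80.5% by the noncentral t, or 81.5% by the normal approximation.

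The stated 80% reproduces. It belongs to the 48-week comparison that the SAP has abandoned.

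**What a reader can already derive for the means.** Per-arm SEs combine as √(SE_A² + SE_B²). With the planning values, SE_A = 8/√50 = 1.13 and SE_B = 8/√25 = 1.60, so the combined SE is √(1.28 + 2.56) = 1.96. An approximate difference and interval therefore follow from the planned tables, but only by arm received.

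**Half-width of the 95% CI for a mean difference.** Formula: t(0.975, nA + nB − 2) × SD × √(1/nA + 1/nB).

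| nA/nB | SD 8 (planned) | SD 16 (assumed) |
|---|---|---|
| 50/25 (planned) | 1.993 × 1.96 = 3.9 | 7.8 |
| 30/15 (assumed) | 5.1 | 10.2 |
| 20/10 (assumed) | 2.048 × 3.10 = 6.3 | 12.7 |
| 10/5 (assumed) | 9.5 | 18.9 |

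With SD 8, the interval reaches further than the 5.6-point design difference on either side once the arms are somewhat smaller than 30/15.

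**Half-width for a difference in proportions.** Formula: 1.96 × √(0.7 × 0.3 × (1/nA + 1/nB)), taking 70% in both arms as an assumption.

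- 50/25: 1.96 × √(0.21 × 0.06) = 0.220, about 22 percentage points.
- 20/10: 1.96 × √(0.21 × 0.15) = 0.348, about 35 percentage points.

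The 50/25 rows are best cases for the 12-week endpoints, which take only subjects with at least 12 weeks of eligible data. These are pooled-t and Wald approximations. The intervals proposed below would differ somewhat, and SD 8 was chosen for 48-week adherence.

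**The case against.** The case on the other side is substantial.

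- **Redaction.** Hidden text sits where a contrast for the means could be specified. This stands: nothing can be called missing for those two endpoints. The label descriptive does not settle it, since a difference with an interval can itself be descriptive.
- **Estimates are given.** A reader might infer that the primary objective gets no estimate at all. The documents do not support that. Section 8.3.2 reports n, mean, SD and SE by arm for both mean endpoints and lists each subject's percentage. What the visible text lacks is a prespecified contrast.
- **The change is open and reasoned.** The SAP attributes it to early termination in sections 3, 5.1 and 8.3.1. The protocol calls the study a pilot and exploratory, section 12.3.1 makes description the default, and SAP 8.3.2 allows further exploratory analyses. This rules out any reading of a concealed change. Those further analyses are unspecified and conditional, however, so they do not fill the gap.
- **An interval can lend false authority.** The 12-week endpoints take only subjects with 12 weeks of eligible duration, which depends on the earlier of the recorded last dose and the last bottle activity. That selection happens after randomisation. The all-subject endpoint mixes unequal durations. This stands: an interval covers sampling error only, so it needs a caveat.

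Readers also cannot rebuild the randomised comparison from tables grouped by arm received if any subject switched.

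**Conclusion.** The point holds in a limited form. For the two 12-week proportions, unredacted text promises a summary table and no arm split, difference or interval, where the protocol had planned an odds ratio with a 95% CI for the proportions with at least 80% adherence. For the two mean-adherence endpoints the gap is conditional on what the redacted text contains, and an approximate difference by arm received can be derived in any case.

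The imprecision that would go unshown is large compared with the 5.6-point design difference: 3.9 points either way at the planned size and 6.3 at 20/10, and about 22 and 35 percentage points for the proportions. These figures rest on SD 8 from the abandoned 48-week endpoint, on assumed sizes below plan, and on an assumed 70%.

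It would go too far to say that the SAP contains no contrast anywhere, or that an interval would by itself answer the objective. The redactions block the first statement and the 12-week selection blocks the second. This is a cheap improvement, not a defect that invalidates the analysis.

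**What to change.** Amend SAP 8.3.2 as follows:

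1. Present both 12-week proportions by arm, with the Arm A minus Arm B difference and a two-sided 95% CI (Newcombe or Miettinen-Nurminen).
2. Add the same difference with a Welch t interval for the two mean-adherence endpoints, unless the redacted text already does so.
3. Show each difference by randomised arm, next to the grouping by arm received that sections 7 and 8.1 require.
4. Label the results descriptive and give no p-value.
5. Add a note that the 12-week endpoints include only subjects with at least 12 weeks of eligible data, and that the interval reflects sampling error and not that selection.

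The cost is an extra row or column, one regrouped analysis and the note. No new data or model is needed. The remaining risk is that readers over-interpret a selected comparison, which the note is there to limit.
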